*Mediation analysis:* We will use modern causal inference methods to investigate the set of mediator measures. If the effectiveness analysis shows significant between group differences in the mediators then we will use parametric regression models to test for effect of mediator on outcome, and the residual direct effect of treatment on outcome. Since all the measures are continuous, the indirect effects are calculated by multiplying relevant pathways and bootstrapping is used to produce valid standard errors for the indirect effects. All analyses will adjust for baseline measures of the mediators, outcome and putative measured confounders, and be tested for moderation by diagnosis. Mediation analyses are potentially biased by measurement error in mediators and hidden confounding between mediators and outcomes; we will build on our previous methodological and applied work in this context to include repeated measurement of mediators and outcomes to account for classical measurement error and baseline confounding. We will investigate the sensitivity of the estimates to these problems and that of unmeasured confounding using instrumental variable (IV) methods with baseline covariate by randomisation interactions as potential instruments.

*Moderation analysis:* We will examine differential treatment effects using the set of moderator measures by extending the intention to treat analysis models to include an interaction term between treatment and each of the moderators separately. We will use bias correction/cross-validation methods to identify robust evidence for individual moderation and for a moderation index, both on the overall effect and also along the steps of the mediation pathway.

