11.3 Mediation and Moderator analyses: (These analyses will be a secondary phase)

If the effectiveness analysis shows significant between group differences on the measures considered as putative mediators (i.e. significant ITT effects when these measures are considered as outcomes), then we will test for mediation of the effect of interventions on primary outcome(s) at 56 weeks through these putative mediators. The analysis will use causal mediation analysis based on parametric regression models (Landau et al, 2013).

This involves estimating a linear model for the mediator with group assignment, baseline CFS (or FSS), baseline mediator, diagnosis and presence/absence of depressive symptoms as covariates, and separately estimating a linear model for CFS (FSS) with the mediator, group assignment, baseline CFS, baseline mediator, diagnosis and presence/absence of depressive symptoms as covariates. The effect of group assignment on the mediator is multiplied by the effect of mediator on CFS (FSS) to estimate the indirect effect, and the effect of interventions on CFS (FSS) in the model including mediator is an estimate of the residual direct effect. The

indirect and direct effects sum to the total effect, and bootstrapping with 1000 replications will be used to obtain valid standard errors for the causal mediation effects. The proportion mediated is the indirect effect divided by the total effect. We will test for moderation of the mediation pathways by primary diagnosis.

Exploratory moderation analyses examined whether the between-group effect on CFS (FSS) was moderated by the following baseline variables: XX. The primary analysis models will be extended by including the moderator, its interaction with group assignment and a three-way interaction with group assignment and time as fixed effects. The difference in between-group effects at each level of the moderator will be calculated using the -margins- command in Stata.

The Moderation and Mediation analyses will be in place of any Subgroup analyses and is planned as a secondary analysis paper.

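### SAP 11.3 defines the proportion mediated with no condition on its denominator, so for a therapy with little or no effect on fatigue the percentage carries no information

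*SAP*

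**What the plan says.** SAP 11.3 has one trigger for mediation analysis: "significant between group differences on the measures considered as putative mediators". Once it is met, "then we will test for mediation of the effect of interventions on primary outcome(s) at 56 weeks through these putative mediators". One linear model is fitted for the mediator and one for the fatigue score. The indirect effect is the product of the group effect on the mediator and the mediator's coefficient in the fatigue model. The group coefficient in that second model is the direct effect. The section adds that the "indirect and direct effects sum to the total effect" and that "bootstrapping with 1000 replications will be used to obtain valid standard errors for the causal mediation effects". It then gives the ratio: "The proportion mediated is the indirect effect divided by the total effect". It has no provision for a total effect near zero, or for indirect and direct effects of opposite sign.

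Protocol 10.2 uses the same trigger ("If the effectiveness analysis shows significant between group differences in the mediators then we will use parametric regression models") but does not mention a proportion mediated. The SAP's mediation table (13.6, Table 10) is still to be completed, so no reporting rule there fills the gap. By contrast, SAP 6.1 does make one analysis depend on a fatigue result: FSS is analysed formally only if the CF effect is positive, and otherwise as exploratory.

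**The concern.** The wording of the test presupposes an effect of the therapy on fatigue, but the trigger does not require one. A therapy could shift a measure such as physical activity and leave CF unchanged. The rule would still produce a percentage for that arm, and the percentage would claim to apportion an effect that has not been shown.

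The protocol's secondary objectives say that mediator findings are to inform the design of future interventions. A figure such as 140% or -60% is visibly odd. A figure of 45% from the same unstable ratio looks credible and is no more informative.

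**Working it through.** **Inputs from the documents.** SAP 10 gives a CF difference of 2, SD 4 (standardised effect 0.50), 2.5% per comparison, 90% power and 100 evaluable per arm. Protocol 5.1 gives 20% dropout. SAP 11.1 gives two-sided 5% for treatment effects, used here for the mediator trigger.

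**Assumed, because the documents give no value.** The therapy's effect on the mediator (0.3 to 0.5 SD in the main range) and the within-arm mediator-fatigue association (0 to 0.5). Baseline covariates and centre clustering are left out.

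**1. The plan's own figure.** n per arm = 2 × (2.2414 + 1.2816)² × (4/2)² = 99.3, so 100. Power at 100 is 90.2%. Then 100/0.80 = 125 per arm, or 375 in total. This reproduces.

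**2. When the ratio leaves 0-100%.** With indirect effect I and direct effect D, the ratio is I/(I + D). It lies between 0 and 1 exactly when I and D have the same sign. For a positive I it leaves that range when the estimated total T = I + D falls below I.

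**3. Approximation by hand.** In SD units the standard error of T is √(2/100) = 0.141. Treating I as known, P(outside) ≈ Φ((I − true total)/0.141), where I = mediator shift × association.

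| True total (SD) | Mediator shift | Association | I | P(outside) |
|---|---|---|---|---|
| 0 | 0.5 | 0.2 | 0.10 | Φ(0.71) = 76% |
| 0 | 0.5 | 0.3 | 0.15 | Φ(1.06) = 86% |
| 0 | 0.5 | 0.5 | 0.25 | Φ(1.77) = 96% |
| 0.2 | 0.5 | 0.4 | 0.20 | Φ(0) = 50% |
| 0.2 | 0.3 | 0.4 | 0.12 | Φ(−0.57) = 29% |
| 0.5 | 0.5 | 0.4 | 0.20 | Φ(−2.12) = 2% |
| 0.5 | 0.5 | 0.5 | 0.25 | Φ(−1.77) = 4% |

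**4. Simulation, among trials passing the mediator trigger.**
- Zero total effect, shift 0.3 to 0.5 SD, association 0 to 0.5: outside 0-100% in about 58-98%.
- True total 0.2 SD, association 0.4: about 50%.
- True total 0.5 SD, as planned: about 3%.

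A separate simulation in CF units (SD 4, mediator shift 0.5 or 0.8 SD, 1,000 trials per scenario) agrees:
- Zero total, mediator unrelated to fatigue: outside in 55-62%; central 95% of ratios from −2.8 to 3.0 (shift 0.5 SD) and −4.1 to 5.6 (shift 0.8 SD).
- Zero total, mediator related to fatigue: outside in 87-99.9%.
- Total of 1 CF unit, half mediated (shift 0.5 SD): outside in 20%; central 95% from −2.0 to 3.4 around a true 0.5.
- Total of 2 CF units, half mediated: outside in 1.6-3.4%; median 0.48-0.50.

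**5. Is the indirect-effect test itself at fault?** With zero total effect and a mediator unrelated to fatigue, the bootstrap interval for the indirect effect excluded zero in 2.9% (shift 0.5 SD) and 6.8% (shift 0.8 SD) of gated trials, near the nominal 5%. With real opposing paths that cancel, it excluded zero in about 99%, correctly. With no causal link but an unmeasured common cause (residual correlation −0.3 or −0.5), it excluded zero in 98-100%. Only the last is spurious mediation, and its source is confounding.

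**6. Effect of a condition on the total.** Suppose the ratio is reported only when the total CF effect is significant at 2.5%. About 2-3% of gated zero-effect trials would then still report one, against 100% under the present rule. With a true 2-unit effect, 92-93% would still report it, and the share outside 0-100% falls to 0.2-0.5%.

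**The case against.** A reader might infer that the SAP never asks whether the therapy changed fatigue, and so would declare mediation of an effect that does not exist. The documents do not support that. SAP 11.2.1 tests each therapy against usual care at 56 weeks, Table 8 reports the result, and 11.3 itself decomposes the total effect. The total effect is estimated; it is only not used as a condition.

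A reader might also infer that a missing total-effect requirement makes the indirect-effect test invalid. It does not. An indirect effect can be real when opposing paths cancel, and step 5 shows near-nominal error when the mediator is unrelated to fatigue. Simulations with zero total effect can show a significant indirect effect in 73-92% of trials. Those rates come from an assumed association of 0.2 to 0.5 and an assumed 0.5 SD mediator shift; they are not false-positive rates. Where such a result is spurious, the cause is mediator-outcome confounding. Protocol 10.2 acknowledges this ("Mediation analyses are potentially biased by measurement error in mediators and hidden confounding between mediators and outcomes") and plans instrumental-variable sensitivity analyses, although SAP 11.3 does not repeat them. Requiring a total effect would not cure confounding.

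Other points on this side also stand. The analysis is a secondary phase intended for a separate paper. SAP 11.3 does not clearly promise a standard error for the ratio. The planned baseline adjustment is missing from the simulations. None of this supplies a condition on the denominator.

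**Conclusion.** The concern holds for the proportion mediated and not for the mediation analysis as a whole. As written, the rule yields a percentage for any arm that passes the mediator trigger, and in a null or weak arm that percentage is uninformative. With zero total effect, about 58-98% of ratios fall outside 0-100%. At a true 0.2 SD the figure is about 50% for a 0.5 SD mediator shift and association 0.4, and by the hand approximation about 29% for a 0.3 SD shift. At the planned 0.5 SD the problem nearly disappears, at about 3%.

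These rates rest on mediator shifts and associations that the documents do not give, and on unadjusted models. The direction does not depend on them, because it follows from dividing by an estimate close to zero. The primary test is untouched. This is an inexpensive correction to a stated secondary rule.

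**What to change.** Add to SAP 11.3, for each therapy and each of CF and FSS:

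- Always report the indirect, direct and total effects with confidence intervals.
- Report the proportion mediated only when the confidence interval for that therapy's 56-week total effect excludes zero, at the level used for the primary comparison, and the indirect and direct effects have the same sign.
- Otherwise, do not describe the measure as mediating an effect of the therapy on fatigue.

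State the level explicitly, since SAP 10 uses 2.5% per comparison and SAP 11.1 uses 5%. Both conditions are needed: a shared sign alone only forces the ratio into 0-100% and does not make it precise. It would also help to carry the Protocol 10.2 confounding sensitivity analyses into SAP 11.3, because this rule does not address confounding.

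The cost is a few sentences. No percentage is reported for an arm without a demonstrated fatigue effect, or where the paths oppose each other. With a true effect of 1 CF unit, only about 33% of gated trials would report one. Those ratios would tend to be low (median 0.32 against a true 0.5), because the condition selects large estimated totals. With a true effect of 2 units this shrinks to a median of 0.46-0.49.

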11.4 Quantitative evaluation Analysis

The main analysis to assess preference on the treatment effect whereby 'no preference' will be considered as being 'not matched' i.e. did not get their preferred treatment.

Two sensitivity analyses will be considered regarding those who 'had no preference'.

- To drop them from the analysis
- To include in the 'matched' group.

Another set of sensitivity analyses will assess the impact of adjusting for 'how positive' participants were about receiving their preferred option, summarised in the table see dummy tables below*. *post randomisation moderator effects such as therapist/HCP effect analyses, patient adherence will be a secondary analysis phase.*

11.5 Missing Outcome Data

The sensitivities of treatment effect estimate to missing outcome data will be explored; these models will explore the robustness of the treatment estimate to whatever small amount of missing data there is. We will follow the strategy outlined in White *et al* (2). The analysis will use all available data that we believe are valid under the assumption of missing at random. The multilevel models used to account for follow-up over time will also internally impute any covariate missingness assuming they are MAR. However, the models only require the outcome variable at baseline as a covariate (when available) as well as the design factors also at baseline and so may be imputed as described above if missingness is substantial. In a trial this is unlikely. Our final estimates at each follow-up will be only for the actual numbers obtained for each of the Outcomes for the primary ITT analyses. If required, that is if the missingness for the primary outcome is >10%, sensitivity analyses will include multiple imputation such as MICE and/or we will explore a range of values for missing data imputed under missing not at random assumptions (such as pattern mixture models); the extent of

missingness will be assessed along with a determination of if the data are MAR or MCAR. In addition, a comparison of baseline characteristics of the responders and non-responders will be conducted with respect to the primary outcome.

11.6 Missing Baseline Data

Data missing at baseline will be reported as such. If required primary and/or secondary outcome data will be imputed with centre specific mean for continuous data and missing binary/categorical data will include a missing indicator, as indicated by current practice²⁰

11.7 Missing items for Derived Variables - Patient Reported Outcome Measures (PROMs):

There are a number of PROM trial data collected using validated questionnaires, some of which are combined into an overall score and/or domain scores. These are indicated by D in table above in the Timing of Outcome Measures (Section 5). Codes developed in-house are checked and validated by an independent statistician using dummy data. Missingness for amalgamated scores will be treated according to decisions made by the Project Team on 21/06/2019 [See section 14 - Appendix] informed by a review of how others have treated missingness for these derived variables.

11.8 COVID-19

The effect of COVD-19 will be explored. In the first instance, periods before, during and after COVID-19 will be summarised using appropriate descriptive statistics and graphical summaries. If need be, formal analysis will be carried out to explore the effect of COVID-19, that may include time of recruitment in relation to UK lock-down (23rd March 2020) and local conditions at the time each outcome is measured. Attempts will be made to account/adjust for the multiple lockdowns and variations of that around the country using emerging methodologies.

12 Technical Details

Protocol version (vs 11) will be consulted for this SAP. All statistical analyses will use stata (vs 15 for DMC's – and vs 16 for the final analyses). All results will be processed directly into PDF/Word from Stata via LaTEX (MiKTeX 2.9 at time of writing) for the DMC's, the use of putdocx commands in Stata 16 for the final Statistical Report.

13 Dummy Tables

13.1 Descriptive Tables

Table 1: Baseline Demographics (potential moderator variables *)

	measures	CBA N =	PEP N=	Usual Care N =
age	*Continuous			
female	(Y) n/N (%)			
marital status*				
Single				
Married				
Widowed				
Divorced				
Separated				
Living with partner/spouse				
employment status*	(Y) n/N (%)			
Working full-time (30 hrs or more per week)				
Working part-time (less than 30 hrs per week)				
Unemployed and looking for work				
Unable to work because of illness or disability				
At home and not looking for paid employment				
Student				
Retired				
other				
level of education *	(Y) n/N (%)			
Secondary school				
Apprenticeship				
Further education college				
University degree				
 Further degree				
ethnicity *	(Y) n/N (%)			
Scottish				
Other British				
Irish				
Other White				
missing				

*Continuous data: n; mean (sd), median (IQR) and (min, max)

	measures	CBA N =	PEP N=	Usual Care N
				=
Overall Health	*Continuous			
Fatigue for > 3 months	(Y) n/N (%)			
Average level of fatigue	Continuous			
Physical Activity (Typical self-reported)	*Continuous			
Thyroid function test	*Continuous			
Urea and electrolytes	*Continuous			
Full blood count	*Continuous			
Serological status	(Y) n/N (%)			
Rheumatoid Factor positive				
Anti-cyclic citrullinated protein (CCP) positive				
Anti-citrullinated protein (ACP) positive				
Anti-bodyDna Positive				
Anti-bodyNuclear Positive				
Anti-Sm Positive				
Anti-Ro Positive				
Anti-La Positive				
HlaB27 Positive				
Serum complement C3 (g/L)	Continuous			
Serum complement C4 (g/L)	Continuous			
Erosive status	(Y) n/N (%)			
Disease duration				
Summary	*Continuous			
>=6 wk	(Y) n/N (%)			

Table 2: Baseline population health characteristics (potential moderator variables *)

*Continuous data n; mean (sd), median (IQR) and (min, max)

Table 3: Baseline variable outcome mea
--

	Measures	CBA N =	PEP N=	Usual Care N =
Primary				
Chalder Fatigue Scale (Likert score) 0-33	*Continuous			
Fatigue Severity Scale (FSS)	*Continuous			
Secondary				
BRAF-MDQ (fatigue) (0-70)	*Continuous			
HADS (anxiety and depression)	*Continuous			
Short Form-12	*Continuous			
Pain numerical rating scale (0-11)	*Continuous			
Sleep problem scale (0-20)	*Continuous			
Work Productivity and Activity Impairment Questionnaire (for all 4 domains)	*Continuous			
Valued Life Activities Scale (short 14 items)	*Continuous			

*Continuous data: n; mean (sd), median (IQR) and (min, max)

Table(s) 4a-c: Variable outcome summaries at follow-up [at weeks a)10, b) 28 and c) 56]

	Measures	CBA N =	PEP N=	Usual Care N =
Primary				
Chalder Fatigue Scale (Combined Likert scores) (0-33)	*Continuous			
Fatigue Severity Scale (FSS)	*Continuous			
Secondary				
BRAF-MDQ (fatigue) (0-70)	*Continuous			
HADS (anxiety and depression)	*Continuous			
Short Form-12	*Continuous			
Pain numerical rating scale (0-11)	*Continuous			
Sleep problem scale (0-20)	*Continuous			
Work Productivity and Activity Impairment Questionnaire (for 4 domains- all)	*Continuous			
Valued Life Activities Scale (short 14 items)	*Continuous			
Global outcome	*Ordinal/ Continuous			

*Continuous data n; mean (sd), median (IQR) and (min, max)

Table(s) 5a-d: Moderators summaries at a) l	baseline [time=0] b) 10, c) 28 and d) 56 weeks as
appropriate		

	measures	time	CBA N =	PEP N=	Usual Care N =
Characteristics					
Overall Health	Categories n/N (%)	all			
Other co-morbidities (Charlson Index)	*Continuous	all			
Disease Activity		all			
DAS28		all			
ASDAS		all			
BILAG for RA		all			
Inflammation CRP ESR	*Continuous	all			
Cognitions and behaviours					
Brief Illness Perception Questionnaire BIPQ (9 items) Item 9 (text) ‡	*Continuous	all			
Behavioural Response to Illness Questionnaire - BRIQ Scale 1 Scale 2 Total	*Continuous *Continuous *Continuous	all			
Clinical					
Presence of fibromyalgia y/n (And the WPI + SSI Score + TOTAL Score) Disease activity (self-reported, 0-10)	(Y) n/N (%) *Continuous *Continuous	0, 56 all			
Quantitative evaluation	Continuous	uii			
Patient preference: Option CBA Option PEP Option Usual No preference	(Y) n/N (%)	0			
Patient adherence (attendance records)	Secondary	0			
Patient engagement & adherence (telephone)	Secondary	0 10 28			
Patent engagement & adherence (therapist view)	Secondary	10 56			
Patent accentability	(Y) n/N(%)	28			
How satisfied with service received? 1:Very satisfied; 2:Mostly satisfied; 3:Indifferent or mildly dissatisfied; 4:Quite dissatisfied; 99:Not answered; Come back to this program? 1:No, definitely not; 2:No, I don't think so; 3:Yes, I think so; 4:Yes, definitely; 99:Not answered; Get the kind of service wanted? 1:No, definitely; 2:No, not really; 3:Yes, generally;					

99.Not answered:		
To what extent did the program meet needs? 1:Almost all of my needs have been met; 2:Most of my needs have been met;		
3:Only a few of my needs have been met; 4:None of my needs have been met; 99:Not answered:		
Recommend this program to a friend? 1:No, definitely not; 2:No, I don't think so;		
3:Yes, I think so; 4:Yes, definitely; 99:Not answered;		
Satisfied with the amount of help received? 1:Quite dissatisfied; 2:Indifferent or mildly dissatisfied; 3:Mostly satisfied; 4:Very satisfied; 00:Net answered;		
 Have the services received helped to deal more effectively with problems? 1:Yes, they helped a great deal; 2:Yes, they helped; 3:No, they really didn't help; 4:No, they seemed to make things worse; 99:Not answered; 		
How satisfied with the service received overall? 1:Very satisfied; 2:Mostly satisfied; 3:Indifferent or mildly dissatisfied; 4:Quite dissatisfied; 99:Not answered;		
Would you come back to this program if needed? 1:No, definitely not; 2:No, I don't think so; 3:Yes, I think so; 4:Yes, definitely; 99:Not answered:		

*Continuous data n; mean (sd), median (IQR) and (min, max)

‡ Summary of Item 1-8 plus overall Score. Also Item 9 indicates causality, BUT will need to be coded and analysed separately (text data) SG : TBC by [name]

† Patent engagement & adherence (therapist view) at 8 weeks forms the CACE variable (if missing the 4 week) reported value to be substituted

13.3 Follow-up timings

Table 7: Summaries of actual follow-up timings

Time perio	od	CBA N =	PEP N=	Usual Care N =	Total
10 weeks	mean (sd)				
	median (IQR)				
	min(max)				
28 weeks	mean (sd)				
	median (IQR)				
	min(max)				
56 weeks	mean (sd)				
	median (IQR)				
	min(max)				

13.4 Primary outcome summaries and model Estimates

Table 8: Primary outcome for Fatigue: Summaries*# and Model results

	CBA N =	PEP N=	Usual Care N =	Effect sizeª	95% CI	p- value	Effect size ^b	95% CI	p- value
Chalder Fatigue	Scale (Con	bined Liker	t score) 0-33 *c						
Baseline									
10wks									
28wks									
56wks (p)									
Fatigue Severity	/ Scale (FSS) *c							
Baseline									
10wks									
28wks									
56wks (^p)									
Baseline									
10wks									
28wks									
56wks (p)									

All models adjusted for their baseline outcome measure, HADS depression subscale >10 at baseline as fixed effects fixed effect with Centre clustering and individuals nested within centres as random effects *Continuous data:n; mean (sd), median (IQR) and (min, max)

Binary x/n (%)

^aMean difference between CBA and Usual care

^b Mean difference between PEP and Usual care

P Primary time point

^cMultilevel mixed-effects generalized linear model (glm) accounting for different time points.

Recall:

- The primary intention to treat analyses will compare PEP + usual care versus usual care alone, and CBA + usual care versus usual care giving effect sizes ^a and ^b
- The main estimate of treatment effect will focus on the 56 weeks after baseline.

- If the effect of intervention is positive on the CF, then the FSS outcome will be formally analysed. Should the intervention have no effect on the CF, then an explorative analysis of the FSS outcome will be performed.
- All analyses and reporting will follow the guidelines of the CONSORT statement developed specifically for social and psychological intervention trials ³
- CACE analysis as a sensitivity analysis will be considered for the primary outcome Chalder Fatigue

